STU#: STU00214445

PROTOCOL TITLE: Low Burden Wearable Sensor System for Diagnosing Obstructive Sleep Apnea Over Multiple Nights: Diagnostic Agreement with Home Sleep Testing

PRINCIPAL INVESTIGATOR:

[name] MD PhD
Chief of Sleep Medicine
Northwestern Memorial Hospital
Professor of Neurology
Northwestern University Feinberg School of Medicine
P: [contact]
Email: [contact]
[name]

Sponsor:

National Heart, Lung, and Blood Institute

Sponsoring company:

Sibel Inc
Representative: [name]., MD, PhD.
[name]
[name]
P: [contact]

Confidentiality Statement

The information in this document contains information that is privileged or confidential and may not be disclosed unless such disclosure is required by applicable laws and regulations. In any event, persons to whom the information is disclosed must be informed that the information is privileged or confidential and may not be further disclosed by them. These restrictions on disclosure will apply equally to all future information supplied to you, which is indicated as privileged or confidential.

STU#: STU00214445

Signature Pages

Principal Investigator(s):

Name: [name] MD PhD
Title: Chief of Sleep Medicine
Northwestern Memorial Hospital
Professor of Neurology
Northwestern University Feinberg School of Medicine
P: [contact]
Email: [contact]
[name]

Date:

Sponsor Company:

Name: [name], PhD
Title: Sibel Health's Chief Operating Officer
[name]
[name]
P: [contact]
Email: [contact]

Date:

STU#: STU00214445

PROTOCOL SUMMARY

| | |
|--|--|
| Protocol Title (Long Title) | Low Burden Wearable Sensor System for Diagnosing Obstructive Sleep Apnea |
| Protocol Number | v.1 |
| Study Duration | 4 to 6 months |
| Setting | Northwestern University and Participant’s Homes |
| Sample Size | A total of approximately 100 subjects may be recruited to achieve at least 30 subjects to complete the study (Home Sleep Testing portion). |
| Main Inclusion Criteria | 
 ● Age >22 years old or older ● Subjects with suspected or confirmed OSA based on history ● Persons with a previous diagnosis of OSA ● Subjects with self-reported symptoms of OSA ● Willingness to give consent and comply with study procedures |
| Objectives: | 
Analysis of diagnostic yield from multiple nights with ANNE Sleep
 
 ● Analysis of agreement for diagnosis of moderate to severe OSA by determining a patient’s Apnea-Hypopnea Index (AHI) wearing the ANNE Sleep system and WatchPAT ONE over one (1) night worn concurrently ● Assessment of usability compared to current HST in the intended population |
| Investigational Product and Planned Use | ANNE™ Sleep System |
| Commercial Available HST Device | WatchPAT ONE |
| Statistical Analysis | Three subsequent nights will be with the ANNE Sleep system alone. Patient preference will be elicited via psychometric surveys for comfort |

STU#: STU00214445

| | |
|--|---|
| | 
and usability comparing ANNE and a commercially available Home Sleep Test (HST). We expect completion of this aim in 6 months. The apnea-hypopnea index (AHI) will be calculated in ranges of 15 – 30 apnea/hypopnea events per hour for moderate OSA and ≥ 30 apnea/hypopnea events per hour for severe OSA. The oxygen desaturation index (ODI), the hourly average number of desaturation episodes, will also be calculated. With a sample size of at least 30, the large amount of within-person data provides high statistical power for all planned analyses, allowing this data set to answer all proposed questions while minimizing study costs and any risk to patients.
 |
|--|---|

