4.1 Primary Outcome Measures

- Analysis of variation between nights of AHI derived from ANNE Sleep system across multiple sleep nights at home
- Analysis of agreement for diagnosis of moderate to severe OSA by determining a patient's Apnea-Hypopnea Index (AHI) wearing the ANNE Sleep system and WatchPAT ONE over one (1) night worn concurrently
- Patient responses on psychometric surveys for comfort and usability comparing ANNE Sleep and WatchPAT ONE

•

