8.2 COMPLETION OF THE STUDY

- (1) After completing data collection, subjects will be given surveys (**Appendix C**) to complete in print material or by email link via a secure online platform managed by Northwestern University (i.e. REDCap).
- (2) Once the surveys and sleep nights are complete, the study coordinator will let the subject know that their participation is complete. The study coordinator will have a phone call with the subject to confirm testing was successful and address any issues if needed.
- (3) Subjects will be instructed to arrange for a time to return the study kit to the research team in person or will be provided with a pre-paid shipping label. A compensation gift card will then be mailed to the subject’s home address or given to them in-person (if they return the study kits in person to the research team).

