7.1.4 Checklist for scheduled events

The study coordinator should review the schedule of events, summarized below:

| | Initial Visit Day: Screening/ Enrollment | ANNE™ and HST Night One | ANNE™ ONLY Night Two, Three, and Four | End of Study* |
|--|---|-----------------------------------|---|---------------|
| Eligibility | X | | | |
| Consent | X | | | |
| Demographics, Medical Hx, STOP-BANG Questionnaire | X | | | |

STU#: STU00214445

| | | | | |
|---|--|---|---|---|
| ANNE™ Sleep | | X | X | |
| HST Sleep | | X | | |
| Sleep Diary | | X | X | |
| Phone follow-up (which may occur up to 1 week after the study) | | | | X |
| Usability Survey | | | | X |
| Adverse Events | | X | | X |

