10. STATISTICAL ANALYSIS

10.1 Sample size

With a sample size of at least 30, the large amount of within-person data provides high statistical power for all planned analyses, allowing this data set to answer all proposed questions while minimizing study costs and any risk to patients.

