12. WITHDRAWAL OF PARTICIPANTS

Participants may end their participation at any time during the study. The study investigators may choose to withdraw a study subject if he or she is unable to use the devices or complete the study procedures. The study investigators may withdraw a patient if they develop skin sensitivity or have a medical complication that precludes wearing of the sensors on the suprasternal notch.

If a subject is withdrawn from the study, they will be asked to return the study kit that is given to them at the start of the study. Unless specifically requested in writing, researchers will maintain and use data from patients that end their participation early.

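### Comfort and usability is a primary outcome, but its only scheduled survey comes at end of study, so people who stop early because of the devices may never be asked

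*Combined protocol and SAP*

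**What the plan says.** All references are to the combined protocol and SAP.

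- **Status of the outcome.** Section 4.1 lists among its three primary outcome measures: "Patient responses on psychometric surveys for comfort and usability comparing ANNE Sleep and WatchPAT ONE". Section 2 sets the usability objective for the population the device is intended for, not for completers.
- **Timing.** Section 8.2: "After completing data collection, subjects will be given surveys". The schedule of events in 7.1.4 agrees, with a mark in the End of Study column and blanks for Night One and Nights Two to Four: "Usability Survey | | | | X".
- **Leaving early.** Section 12: "The study investigators may choose to withdraw a study subject if he or she is unable to use the devices". It also allows withdrawal for skin sensitivity. Of withdrawn subjects it says "they will be asked to return the study kit"; it mentions no exit survey. Data already collected from early leavers are kept and used unless the subject objects in writing.
- **Partial completion.** Section 11 pays $50 to subjects who do the combined night and one ANNE-only night, together with surveys belonging to those nights. It does not name the surveys.
- **Numbers.** The Protocol Summary states: "A total of approximately 100 subjects may be recruited to achieve at least 30 subjects to complete the study". Section 10 gives no dropout rate, and no analysis set or missing-data rule for the survey.

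**The concern.** Inability to use the devices and skin sensitivity are usability and comfort failures in themselves. If they lead to withdrawal, and the survey comes only after data collection ends, responses go missing for reasons tied to what the survey measures. Keeping the data of early leavers does not help when the survey was never given.

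The study is run at home. Subjects apply the sensors, pair them, operate two applications and download the data themselves (8.1.3, 8.1.4). Failure to manage this is a realistic finding that a usability outcome should capture. At stake is whether the reported result describes the intended population or only those who got to the end.

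**Working it through.** **1. The plan's own figure.** Inputs: about 100 recruited and at least 30 completing (Protocol Summary). With n recruited = completers / (1 − d), 100 = 30 / (1 − d) gives d = 1 − 30/100 = 0.70. The plan states no d, so 100 cannot be reproduced from stated inputs. For comparison, d = 0.10, 0.20, 0.30 and 0.50 would give 34, 38, 43 and 60. The 0.70 is a ceiling on planned non-completion from all causes.

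**2. Who is surveyed under the written schedule.**

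- *Completes all four nights:* surveyed at End of Study (8.2, 7.1.4).
- *Stops after the combined night and one ANNE-only night:* unclear. Section 11 expects some surveys. They could be the Appendix A diaries, which cover sleep, naps, alcohol, caffeine and sleep medication and ask nothing about the devices apart from a free comment line.
- *Tries a device but stops before a second night:* no usability survey is scheduled, and section 11 does not reach this group.
- *Withdrawn for inability to use the devices or for skin sensitivity:* section 12 schedules none.
- *Recruited but never wore a sensor:* has no usability response to lose.

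The gap therefore concerns people who tried a device and left early. The documents do not say how many to expect.

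**3. Illustration of sensitivity.** Assumptions, none from the documents: 24 of 30 completers rate the device favourably (80%), and m further people tried a device but were not surveyed. Counting all m as unfavourable, then all as favourable, the share among everyone exposed lies between 24/(30 + m) and (24 + m)/(30 + m):

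- m = 0: 24/30 = 80% (Wilson 95% interval 62.7% to 90.5%)
- m = 5: 24/35 = 68.6% to 29/35 = 82.9%
- m = 10: 24/40 = 60.0% to 34/40 = 85.0%
- m = 20: 24/50 = 48.0% to 44/50 = 88.0%

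The Wilson interval reflects sampling error among completers only and makes no allowance for people not asked. If instead a share q of the unsurveyed would have been favourable, the overstatement is L × (0.80 − q), where L = m/(30 + m). With m = 10, L = 0.25. For assumed q of 0.65 and 0.50 this gives 0.25 × 0.15 = 3.75 points and 0.25 × 0.30 = 7.5 points. Surveying everyone who tried a device (m = 0) removes the uncertainty.

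**The case against.** Several points on the other side have force.

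- **The 100 and the 30.** A reader might infer that the sponsor expects up to 70% to be lost to the devices. At L = 0.70, the same assumed rates give an overstatement of 0.70 × 0.15 = 10.5 to 0.70 × 0.30 = 21 points. The documents do not support this. Recruitment runs through warehouse searches, referrals and flyers, and the target is a minimum. The other 70 may be screen failures, people who never scheduled a night, or completers beyond 30. This objection stands in full.
- **Section 11.** Two-night subjects may be surveyed. That is possible, but the surveys are unnamed, 8.2 and 7.1.4 schedule no usability survey before the end, and anyone stopping earlier is not covered.
- **Silence is not prohibition.** Section 12 does not say that kit return is the only step, and the end of data collection in 8.2 could mean the end of that subject's own collection. This is a fair reading, but nothing in the text secures it.
- **Other capture.** Section 14 records study-related adverse events and the timing of discontinuation. It does not capture comfort, ease of application or preference.
- **Direction.** The outcome compares two devices, and section 12 refers to the devices in the plural. Losing someone defeated by WatchPAT ONE would move the comparison the other way. Selection toward people who tolerated the devices is a sound inference; a bias in favour of ANNE in the comparison is not established.
- **Diagnostic yield.** A reader might infer that failed nights also drop out of the yield denominator. No section defines that denominator or says that failed nights are excluded.

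**Conclusion.** The point holds as a gap in survey timing. For a primary outcome, the written schedule provides no usability survey for people who try a device and leave early, including those withdrawn for reasons of usability or comfort. The result can be selected toward those who tolerated the devices. Neither the size of the selection nor its direction for the ANNE versus WatchPAT ONE comparison can be derived from the documents. The bounds in the working rest on an assumed 80% among completers and assumed numbers unsurveyed; they show only that a modest number of missing responses would matter with 30 completers. Sections 8.2, 7.1.4, 11 and 12 need reconciling whatever the true number.

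**What to change.** - **Timing.** In 8.2, 7.1.4 and 12, give the usability survey after Night One and again at end of study or at early termination. Night One is when both devices have just been worn. WatchPAT ONE is not worn again, the nights need not be consecutive, and the target window is 8 weeks from enrollment (8.1.2), so an end-only survey may rely on recall over weeks.
- **Section 11.** Name the surveys that go with the two-night payment so that they agree with the revised schedule.
- **Primary response.** Name the Night One response, or the exit response if earlier, as primary for the ANNE versus WatchPAT ONE comparison.
- **Analysis set.** Analyse usability in everyone who attempted to use a device, with completers as a secondary set. Report the numbers recruited, exposed and surveyed, with reasons for stopping.
- **Failed nights.** Report them by cause. Count an attempted night with unusable data as a test failure. Do not count nights never attempted, since these include scheduling lapses and unrelated withdrawals.

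This needs one more REDCap trigger and some wording, and leaves the withdrawal criteria and device use unchanged. The cost is a few extra minutes per subject and possibly a less favourable usability figure. It should be in place before data collection, because answers from people who have left cannot reliably be recovered later.

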1. LIST OF ABBREVIATIONS

| | |
|---------|--|
| AASM | American Academy of Sleep Medicine |
| AHI | Apnea-Hypopnea Index |
| ECG | Electrocardiogram |
| EDF | European Data Format |
| EDW | Electronic Data Warehouse |
| EHR | Electronic Health Record |
| EMG | Electromyography |
| GCP | Good Clinical Practice |
| HIPAA | Health Insurance Portability and Accountability Act of 1996 |
| HR | Heart Rate |
| HST | Home Sleep Test |
| ICF | Informed Consent Form |
| ICH-GCP | International Conference on Harmonization Good Clinical Practice |
| IRB | Institutional Review Board |
| MRN | Medical Record Number |
| NMH | Northwestern Memorial Hospital |
| NPV | Negative Predictive Value |
| OSA | Obstructive Sleep Apnea |
| ODI | Oxygen Desaturation Index |
| PAP | Positive Airway Pressure |
| PAT | Peripheral Arterial Tonometry |
| PHI | Protected Health Information |
| PI | Principal Investigator |
| PPV | Positive Predictive Value |

STU#: STU00214445

| | |
|-------|--|
| PSG | Polysomnography |
| RPSGT | Registered Polysomnography Technicians |
| RR | Respiratory Rate |
| SDB | Sleep Disordered Breathing |
| SL | Sleep Latency |
| SoC | System-on-Chip |
| TST | Total Sleep Time |

2. OBJECTIVES:

The main objective of this study are as follows:

- Analysis of diagnostic yield from multiple nights with ANNE Sleep
- Analysis of agreement of diagnosis of moderate to severe OSA by determining a patient's Apnea-Hypopnea Index (AHI) wearing the ANNE Sleep system and WatchPAT ONE over one (1) night worn concurrently
- Assessment of usability compared to current HST in the intended population

3. INTRODUCTION

Sleep disordered breathing (SDB) is an increasingly common disorder characterized by a pathological increase in upper airway resistance experienced during sleep that ranges from benign snoring to its most severe form of obstructive sleep apnea (OSA). OSA is characterized by recurrent episodes of cessation of breathing and physiological stress as a result of intermittent periods of hypoxemia, and arousals. Studies have demonstrated that OSA leads to profound sleep fragmentation, disturbance of the autonomic nervous system, insulin resistance, increased systemic inflammation, oxidative stress, and subsequent vascular endothelial dysfunction. These physiologic changes cause significant morbidity; OSA is an independent risk factor for wide ranging adverse health outcomes including cardiovascular disease (hypertension, stroke, myocardial infarction), metabolic disorders (insulin insensitivity, diabetes), neurological (dementia), motor vehicle accidents, and mood disorders.¹⁻⁵

The ANNE™ Sleep system has been validated as a diagnostic aid for moderate to severe OSA in a multi-center, open-label clinical study with n=225 subjects. Subjects wore PSG and ANNE Sleep concurrently for one supervised night at a sleep center. Both PSG and ANNE Sleep data were manually scored by 3 blinded registered polysomnography technicians. If AHI values determined by the 3 scorers exhibited great than 15% variation, a board-certified Sleep Medicine physician reviewed the raw data independently per AASM guidelines to account for interscorer variability. The results of the study indicate that ANNE Sleep is sufficiently accurate as an aid to diagnosis of moderate to severe OSA with sensitivity and specificity of 90% and 98% respectively.

4. STUDY ENDPOINTS:

STU#: STU00214445

4.1 Primary Outcome Measures

- Analysis of variation between nights of AHI derived from ANNE Sleep system across multiple sleep nights at home
- Analysis of agreement for diagnosis of moderate to severe OSA by determining a patient's Apnea-Hypopnea Index (AHI) wearing the ANNE Sleep system and WatchPAT ONE over one (1) night worn concurrently
- Patient responses on psychometric surveys for comfort and usability comparing ANNE Sleep and WatchPAT ONE

•

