8.1.2 Initial Visit Day: Screening/Enrollment

The subject will have the option to discuss with the study coordinator over the phone or by a Zoom teleconference from the subject's personal device. If Zoom communication is selected a unique meeting number and password known only to the subject will be provided. The study coordinator will monitor the number of attendees in the meeting and restrict meetings to IRB approved researchers on this study, the study subject, and additional people at the subject's discretion. Researchers will host the Zoom sessions and will utilize the waiting room feature to ensure that only the appropriate participants are included on the call.

The study coordinator will cover following topics associated with the study during the Screening/Enrollment visit:

STU#: STU00214445

- (1) Informed Consent will be reviewed and signed electronically using REDCap.
- (2) The qualified subject will be asked to schedule a study date to participate at home. The nights of sensor wear do not need to be consecutive. Subjects will be instructed to set-up both devices on Night One of sleep testing and then only the ANNE device on Nights 2-4.
One Night = HST and ANNE Sleep
3 Additional Nights = ANNE Sleep only
The target time frame will be to complete the sleep nights within 8 weeks of enrollment.
- (3) Subjects will be advised to avoid alcohol and sleep medication use such as antihistamine (OTC) or prescribed medicines for sleep support on the testing night. Any use of these substances on the night of monitoring sleep will be asked to be recorded in the diary.
- (4) Subjects will be informed how to complete the Demographic, Medical History and Sleep Survey sleep diary and usability survey (**Appendix A-C**). The surveys should be available to complete via an email link through REDCap or printed out forms.

Any subject's questions or concerns associated with the study will also be addressed.

At least 24 hours prior to the subject's sleep nights, the study coordinator will contact the participant by phone to confirm their planned sleep study nights at home.

The below sections describe the procedures for setting up the ANNE and HST devices, respectively.

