10.2 Apnea-hypopnea index (AHI) and oxygen desaturation index (ODI)

1. AHI will be calculated in ranges of 15 – 30 apnea/hypopnea events per hour for moderate OSA and ≥ 30 apnea/hypopnea events per hour for severe OSA. Continuous variables of AHIs during ~~three~~four-night study will be summarized using tables of descriptive statistics. The AHIs with variables will be summarized using counts and percentages. Descriptive statistics will be presented by diagnosis.
2. Diagnostic outcomes will be tabulated and compared for ANNE Sleep vs WatchPAT ONE.
3. Patient preference will be elicited via psychometric surveys for comfort and usability comparing ANNE and WatchPAT ONE.

STU#: STU00214445

4. The oxygen desaturation index (ODI), the hourly average number of desaturation episodes, will also be calculated.

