| 14b. If yes, list medication(s), dose, and time taken. | Medication(s): Relaxo-Herb Dose: 50 mg Time(s) taken: | Medication(s): Dose: Time(s) taken: |
| 15. Comments (if applicable) | I have a cold | |

STU#: STU00214445

**APPENDIX B –
APNEAS ANNE Sleep Sensor Survey**

Subject #: _____

Date: ____/____/____

Thank you for participating in wearing the ANNE Sleep system. This survey helps researchers better understand your experience with wearing sensors and helps develop and improve them for future patients. Please provide one answer to each of the following questions. You can skip any questions you do not know the answer to or do not want to answer.

1. Overall, all of the the sleep study sensors were comfortable for me to sleep with:
 Strongly Agree Agree Neither agree or disagree Disagree Strongly Disagree

2. Overall, ANNE Sleep sensors were comfortable for me to sleep with:
 Strongly Agree Agree Neither agree or disagree Disagree Strongly Disagree

3. How quickly you fell asleep comparing to typical nights for you
 Much Slower Slower About the same Faster Much Faster

4. The ANNE Sleep Sensors would be more comfortable to other sleep sensors
 Strongly Agree Agree Neither agree or disagree Disagree Strongly Disagree

5. The **application** of the ANNE Sleep Sensors was easy and comfortable.
 Strongly Agree Agree Neither agree or disagree Disagree Strongly Disagree

6. The **removal** of the ANNE Sleep Sensors was easy and comfortable.
 Strongly Agree Agree Neither agree or disagree Disagree Strongly Disagree

7. Using wireless ANNE Sleep Sensors would be easy to do at home.
 Strongly Agree Agree Neither agree or disagree Disagree Strongly Disagree

8. Please describe how the **wireless Chest sensor** felt while sleeping.

STU#: STU00214445

Very uncomfortable Uncomfortable No change Comfortable Very comfortable

9. Please describe how the **wireless Limb sensor** felt on your finger while sleeping.

Very uncomfortable Uncomfortable No change Comfortable Very comfortable

10. Please indicate if you experienced the following while wearing the **wireless sensors**:

Redness Irritation Both None

11. Having my sleep data collected at home and sent to my doctor would be more convenient for me.

Strongly Agree Agree Neither agree or disagree Disagree Strongly Disagree

12. I could see myself using ANNE Sleep at home to monitor my breathing while I sleep.

Strongly Agree Agree Neither agree or disagree Disagree Strongly Disagree

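### The third primary outcome compares comfort and usability of ANNE Sleep with WatchPAT ONE, but the only device survey visible in the documents collects no WatchPAT ONE rating and no comparative usability response

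*Combined protocol and SAP*

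**What the plan says.** The comparison is promised in three places. Section 2 (Objectives) and the Protocol Summary include "Assessment of usability compared to current HST in the intended population". Section 4.1 lists "Patient responses on psychometric surveys for comfort and usability comparing ANNE Sleep and WatchPAT ONE" as the third of three primary outcomes. Section 10.2 states that "Patient preference will be elicited via psychometric surveys for comfort and usability comparing ANNE and WatchPAT ONE", with no score or method of comparison.

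On the form itself, section 8.1.2 says "Subjects will be informed how to complete the Demographic, Medical History and Sleep Survey sleep diary and usability survey" and refers to Appendices A to C. Appendix A is a sleep diary. Appendix C holds demographics, medical history and another diary. Appendix B is a 13-item sensor survey titled for ANNE. It opens with "Thank you for participating in wearing the ANNE Sleep system" and tells subjects "You can skip any questions you do not know the answer to or do not want to answer". Section 8.2 sends subjects to Appendix C for the end-of-study surveys, but Appendix C has no item about either device.

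On exposure and timing, section 8.1.2 says "Subjects will be instructed to set-up both devices on Night One of sleep testing and then only the ANNE device on Nights 2-4" and "The target time frame will be to complete the sleep nights within 8 weeks of enrollment". The schedule of events (numbered 7.1.4, after section 8.2) marks the usability survey once, at End of Study.

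**The concern.** A comparison of two devices needs a response about each device, or a direct question that sets one against the other. Appendix B asks about ANNE in detail and never asks about WatchPAT ONE. If the form is used as it stands, the results could describe how subjects found ANNE. Any statement that ANNE is easier to use than WatchPAT ONE would have no data behind it, and a statement about comfort would rest on very little. Responses that were not collected cannot be recovered at analysis. A larger sample does not help, because the gap lies in the questions.

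**Working it through.** No sample-size figure can be reproduced for this outcome: section 10.1 gives at least 30 subjects, with no effect size, SD, alpha or margin. The check is a count of what Appendix B asks.

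**Step 1. Classify the 13 items.**

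| Class | Items | Count |
|---|---|---|
| ANNE alone, named | 2, 5, 6, 7, 12 | 5 |
| ANNE alone, inferred | 8, 9, 10 | 3 |
| WatchPAT ONE alone | none | 0 |
| All sensors pooled | 1 | 1 |
| Comparative | 4 | 1 |
| Neither device | 3, 11 | 2 |
| Free text | 13 | 1 |

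Total: 5 + 3 + 0 + 1 + 1 + 2 + 1 = 13.

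Items 8 to 10 do not name ANNE. They refer to wireless sensors, and items 8 and 9 use ANNE's component names, Chest and Limb. Section 7 describes the WatchPAT ONE finger sensor as wired, and section 8.1.4 has its chest sensor threaded through the sleeve. Counting only named items gives 5 instead of 8, and the WatchPAT ONE count stays at 0.

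**Step 2. What can be compared.**
- Usability: items 5, 6, 7 and 12 bear on it, all for ANNE only. Comparative usability responses: 0 items × 30 = 0.
- Comfort, direct: item 4 only. At most 1 × 30 = 30 responses, fewer if skipped. The comparator is unnamed other sensors, the wording is hypothetical and favours ANNE, and the response scale is symmetric. WatchPAT ONE is the only other system worn in the study. However, section 5.1.1 admits people with a previous OSA diagnosis, some of whom may have an earlier test in mind.
- Comfort, indirect: item 2 (ANNE) beside item 1 (all sensors). Item 1 includes ANNE, and WatchPAT ONE is worn only together with ANNE. A lower score on item 1 could reflect WatchPAT ONE or the burden of wearing both.

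**Step 3. Exposure before the survey.** Up to 4 ANNE nights against 1 shared WatchPAT ONE night, and 0 nights with WatchPAT ONE alone. Night One precedes the last night by 3 days if the four nights are consecutive. The gap is about 8 × 7 = 56 days if Night One directly follows enrollment and the target is just met. The 56 days are an extreme case, and the target is not a limit.

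**Step 4. What matched items would give.** The half-width of a 95% CI for a mean paired difference is t(0.975, n−1) × SD / √n. The SDs are assumptions; the documents give none. The case of 25 pairs allows for skipped items.

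| Pairs | t / √n | SD 0.8 | SD 1.0 | SD 1.5 |
|---|---|---|---|---|
| 30 | 2.045 / 5.477 | ±0.30 | ±0.37 | ±0.56 |
| 25 | 2.064 / 5 | ±0.33 | ±0.41 | ±0.62 |

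For a preference proportion with 30 respondents, the widest exact 95% CI (15/30) is 31.3% to 68.7%. The denominator matters. In an illustrative split of 12 ANNE, 6 WatchPAT ONE and 12 no preference, the ANNE share is 12/30 = 40.0% (22.7% to 59.4%). Leaving out those with no preference makes it 12/18 = 66.7% (41.0% to 86.7%).

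**The case against.** The strongest reply is that the visible text may be incomplete. Part of the text between Appendix F and the scoring manual was not available, and section 8.2 points to an appendix that does not fit, so the wrong form may have been attached. This stands as a condition on the conclusion. Against it, section 8.1.2 places the usability survey within Appendices A to C, all of which are visible, and only Appendix B matches.

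A reader might infer that the usability half of the outcome has no data. The documents do not support that: items 5, 6, 7 and 12 collect usability data for ANNE. Only the comparison is missing. Nor is comfort confined to a single one-sided question. Item 4 lets a subject disagree strongly, and item 2 can be set beside item 1, weak as that contrast is.

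A reader might also infer that asking once at the end biases the answers towards ANNE. Unequal exposure and recall make this possible, but nothing in the documents sizes it. Section 11 pays two-night completers for nights with accompanying surveys, which may mean diaries or an earlier usability form, so even the single timing is not certain.

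Adverse events are scheduled on Night One, so skin reactions to WatchPAT ONE may be partly captured. That does not supply comfort or usability ratings. Finally, the plan states no test for this outcome and may intend only description. Description of a comparison still needs responses about both devices.

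**Conclusion.** The concern holds, conditional on no other form existing outside the visible text. On that condition, a listed primary outcome could not be reported as the comparison it is defined to be: there would be 0 WatchPAT ONE ratings and 0 comparative usability responses whatever the sample size. Comfort would rest on item 4 and an indirect contrast of items 2 and 1. The item count depends on one inference (items 8 to 10), which does not change the conclusion. Timing is a secondary point of unknown size. The analyses of AHI variation between nights and of diagnostic agreement are untouched. This should be settled before further subjects complete the survey.

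**What to change.** 1. If a WatchPAT ONE form exists, attach and cite it. Otherwise add to Appendix B a WatchPAT ONE counterpart for each ANNE-only item, with the same wording and scale apart from the device name. Drop the word wireless from items 7 to 10 and word item 7 as experienced.
2. Split items 5 and 6, which ask about ease and comfort together, into separate questions for both devices. Without this, ease of use is not isolated.
3. Replace item 4 with a neutral choice: ANNE Sleep, WatchPAT ONE or no preference. Report all three proportions, with exact 95% CIs, over everyone who answered that question.
4. Give the two-device items the morning after Night One, so that recall is similar for both devices and subjects who stop early contribute. The End of Study survey can stay for ANNE.
5. Report paired differences, for example for ease of application, with 95% CIs and the counts rating ANNE higher, equal and lower. Cross-tabulate item 10, which is categorical. State as a limitation that WatchPAT ONE is worn only together with ANNE, so sleep comfort and chest-site skin reactions are only partly attributable to one device.
6. Reconcile the Appendix B and Appendix C references in section 8.2.

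Cost: the split turns 8 ANNE items into 10, with 10 counterparts. With the 5 other items (1, 3, the new 4, 11, 13) the full set is 25 instead of 13. That means a few minutes of subject time, one extra survey link and IRB approval of the revised form.
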